1.4. Potential Risks of the Combination Regimens

The principal toxicities of administering agents that modulate the immune system are irAEs, including skin manifestations, pneumonitis, enterocolitis, and endocrinopathies. Immune-related AEs have been reported in subjects treated with nivolumab and ipilimumab. As the use of immunotherapies become more prevalent, guidelines for the management of irAEs continue to evolve. Careful monitoring, early diagnosis, and treatment with corticosteroids for more severe events is recommended. The time of onset of irAEs varies, with skin manifestations and GI toxicity seen early and elevated liver enzymes and endocrinopathies appearing later ([Weber et al 2015](#)). Subjects enrolled in this study will be carefully monitored for the onset of irAEs, and guidelines for the management of these toxicities are provided in the Protocol and in the prescribing information for nivolumab and ipilimumab.

INCAGN01949 was well-tolerated in toxicology studies in cynomolgus monkeys at several doses and has been well-tolerated at doses explored so far in the Phase 1 clinical study (INCAGN 1949-101). No subjects discontinued due to a treatment-related toxicity. Adverse events were generally mild and managed with supportive care. However, as INCAGN01949 is an immune stimulator, it may enhance or exacerbate irAEs associated with any immune therapy.

The risks of nivolumab and ipilimumab are well-characterized and described in more detail in Section 1.3. Of note, a lower dose and less frequent administration of ipilimumab (1 mg/kg Q6W) was selected for the doublet and triplet combinations to minimize AEs based on emerging safety data with the nivolumab and ipilimumab combination ([Antonia et al 2016](#), [Hellmann et al 2016](#)).

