4. INVESTIGATIONAL PLAN

4.1. Overall Study Design

Based on a change in the development plan for INCAGN01949, enrollment to the study was stopped after 52 subjects were enrolled. Phase 2 of this study will not open for enrollment. Continued study treatment will be permitted for up to 24 months at the discretion of the investigator for subjects who are considered to be obtaining ongoing clinical benefit.

[figure not shown]
This is an open-label, nonrandomized, Phase 1/2 study to determine the safety, tolerability, and efficacy of INCAGN01949 when given in combination with immune therapies. Phase 1 will consist of 2 parts. Dose escalation (Part 1) will consist of a 3 + 3 + 3 design to determine the MTD, or PAD, defined as a dose that provides a maximal biochemical effect [REDACTED] of INCAGN01949 when given in combination with immune therapies. The safety expansion (Part 2) will further explore tolerated doses of INCAGN01949 given as a run-in of 2 doses followed by concomitant immune therapies. Subjects with advanced or metastatic cervical cancer, endometrial cancer, gastric cancer (including stomach and GEJ), esophageal cancer, HCC, melanoma, Merkel cell carcinoma, mesothelioma, MSI-H CRC, NSCLC, ovarian cancer, SCCHN, SCLC, RCC, TNBC, and urothelial carcinoma who have progressed after treatment with available therapies that are known to confer clinical benefit or who are intolerant to treatment will be enrolled in both parts of Phase 1.

The Phase 2 expansion will further evaluate the safety, tolerability, and efficacy of immune therapies combined with INCAGN01949 in 2 different parts. In Phase 2 Part A, the selected doses of INCAGN01949 will be combined with nivolumab in PD-1/L1 refractory subjects with advanced or metastatic gastric cancer, SCCHN, NSCLC, and RCC to further explore the safety and efficacy of different doses of INCAGN01949 in combination with nivolumab in this population. Phase 2 Part B will evaluate the recommended dose(s) of INCAGN01949 in combination with nivolumab (and ipilimumab where applicable). PD-1/L1 refractory subjects with advanced or metastatic gastric cancer, SCCHN, NSCLC, or RCC will also be enrolled in Phase 2 Part B. Pretreatment biopsies will be mandatory for subjects enrolled into either part of Phase 2. On-treatment biopsies will be optional.

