9. STATISTICS

Based on a change in the development plan for INCAGN01949, enrollment to the study was stopped after 52 subjects were enrolled into Phase 1. Therefore, only Phase 1 statistical analyses will be performed.

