2. STUDY INFORMATION, OBJECTIVES, AND ENDPOINTS

2.1. Protocol and Case Report Form Version

This SAP is based on INCAGN 1949-201 Protocol Amendment 1 dated 14 JUN 2017 and CRFs approved 04 OCT 2017. Unless superseded by an amendment, this SAP will be effective for all subsequent Protocol amendments and CRF versions.

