8.2.4. Adverse Event Summaries

An overall summary of AEs by treatment group and by tumor type as applicable will include the following:

- Number (%) of subjects reporting any TEAEs
- Number (%) of subjects reporting any DLTs
- Number (%) of subjects reporting any SAEs
- Number (%) of subjects reporting any Grade 3 or higher TEAEs
- Number (%) of subjects reporting any TEAEs related to INCAGN01949
- Number (%) of subjects reporting any TEAEs related to nivolumab
- Number (%) of subjects reporting any TEAEs related to ipilimumab
- Number (%) of subjects who temporarily interrupted INCAGN01949 because of TEAEs
- Number (%) of subjects who temporarily interrupted nivolumab because of TEAEs
- Number (%) of subjects who temporarily interrupted ipilimumab because of TEAEs
- Number (%) of subjects who permanently discontinued INCAGN01949 because of TEAEs
- Number (%) of subjects with INCAGN01949 dose reductions because of TEAEs
- Number (%) of subjects who had a fatal TEAE
- Number (%) of subjects who withdrew from study because of an TEAE

The following summaries will be produced by MedDRA term:

- Summary of TEAEs by SOC and PT
- Summary of TEAEs by PT in decreasing order of frequency
- Summary of TEAEs by SOC, PT, and maximum severity
- Summary of Grade 3 or higher TEAEs by SOC and PT
- Summary of INCAGN01949 treatment-related AEs by SOC and PT
- Summary of nivolumab treatment-related AEs by SOC and PT
- Summary of ipilimumab treatment-related AEs by SOC and PT
- Summary of Grade 3 or higher INCAGN01949 treatment-related AEs by PT in descending order of frequency
- Summary of Grade 3 or higher nivolumab treatment-related AEs by PT in descending order of frequency

- Summary of Grade 3 or higher ipilimumab treatment-related AEs by PT in descending order of frequency
- Summary of treatment-emergent SAEs by SOC and PT
- Summary of treatment-emergent SAEs by PT in descending order of frequency
- Summary of treatment-emergent non-SAE by SOC and PT.
- Summary of treatment-related SAEs by SOC and PT
- Summary of TEAEs leading to INCAGN01949 dose reduction by SOC and PT
- Summary of TEAEs leading to INCAGN01949 dose interruption by SOC and PT
- Summary of TEAEs leading to nivolumab dose interruption by SOC and PT
- Summary of TEAEs leading to ipilimumab dose interruption by SOC and PT
- Summary of TEAEs leading to discontinuation of INCAGN01949 by SOC and PT
- Summary of TEAEs leading to death by SOC and PT

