3.2.27.1	Summary of Grade 3 or Higher Treatment-Emergent Immune-Related Adverse Events (Investigator Identified) by MedDRA System Organ Class and Preferred Term – by Treatment Group and Dose	Phase 1 FAS Population		X
3.2.27.2	Summary of Grade 3 or Higher Treatment-Emergent Immune-Related Adverse Events (Investigator Identified) by MedDRA System Organ Class and Preferred Term – by Treatment Group and Tumor Type	Phase 2 FAS Population		X
3.2.28	Life Table Estimate of Time to First Grade 3 or Higher Treatment-Emergent Adverse Event – by Treatment Group and Tumor Type	Phase 2 FAS Population	X	
3.2.29.1	Summary of Adverse Events With a Fatal Outcome by System Organ Class and Preferred Term – by Treatment Group and Dose	Phase 1 FAS Population	X	
3.2.29.2	Summary of Adverse Events With a Fatal Outcome by System Organ Class and Preferred Term – by Treatment Group and Tumor Type	Phase 2 FAS Population	X	

Table No.	Title	Population	Standard	In-Text
3.2.30.1	Summary of Infusion Reactions – by Treatment Group and Dose	Phase 1 FAS Population		
3.2.30.2	Summary of Infusion Reactions – by Treatment Group and Tumor Type	Phase 2 FAS Population		

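### The one planned time-to-onset safety table is assigned to Phase 2, which will be empty; re-assigning it to Phase 1 is a cheap improvement, because the Phase 1 adverse event tables give only number (%) and ignore unequal time at risk

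*SAP*

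**What the plan says.** SAP Appendix A, Section 3.2, lists Table 3.2.28 as "Life Table Estimate of Time to First Grade 3 or Higher Treatment-Emergent Adverse Event", split by treatment group and tumour type, and gives its population as the Phase 2 full analysis set. Among Tables 3.2.1 to 3.2.30 it is the only one without a Phase 1 version. SAP 8.2.4 does not mention it and describes counts such as "Number (%) of subjects reporting any Grade 3 or higher TEAEs", plus tables by organ class, preferred term and severity. The safety figures are laboratory plots. Exposure (SAP 6.4) is summarised as infusions and dose, with no person-time or exposure-adjusted event rate.

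Protocol 4.1 states "Phase 2 of this study will not open for enrollment", and Section 9 adds "Therefore, only Phase 1 statistical analyses will be performed". SAP 2.1 says that, unless amended, "this SAP will be effective for all subsequent Protocol amendments and CRF versions", and SAP Table 14 lists only the original version of 06 FEB 2018. The table therefore drops out by default. No text records a decision to omit it.

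Time at risk varies by design. Treatment is capped at 24 months (Protocol 5.5.1). New events are collected for at least 60 days after the last dose or until new anticancer therapy, whichever is first (Protocol 6.4). Protocol 1.4 says "The time of onset of irAEs varies, with skin manifestations and GI toxicity seen early" and places liver enzyme and endocrine effects later. Protocol 5.4.7 adds that immune-related events can appear months after the last dose.

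**The concern.** A crude percentage counts a subject who left after one month as event-free on the same footing as one followed for two years. It is not a risk at any stated time, and two groups with the same toxicity can show different percentages because one stayed on treatment longer.

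Safety and tolerability are the primary Phase 1 objective, and the safety report on the 52 enrolled subjects is the study's main product. Protocol 5.4.2 also allows toxicity seen after the 28-day window to lower the maximum tolerated dose. A reader will want to know how often severe events occur by a given month, and no planned Phase 1 table says so.

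**Working it through.** The plan states no figure on this point, so there is nothing to reproduce. The check is a search of the planned outputs and an illustration of size.

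**Search.** SAP Sections 8.1 to 8.5, Appendix A Tables 3.1 to 3.5, Figures 4.1 and 4.2, Listings 2.6 and Protocol 9.4.2 were read for any Phase 1 output with a time element. The infusion-reaction summary (SAP 8.2.3.2) shows study day and onset date, but these are acute events. Listings 2.6.2, 2.6.3 and 2.6.9 cover adverse events, dose-limiting toxicities and immune-related events subject by subject. No table estimates risk over time.

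**Illustration.** From the documents: 24-month cap; about 2 months of collection after treatment. Assumed: the same constant hazard in every group with 40% risk at 12 months, and exponential treatment time with median m.

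- Hazard: h = −ln(0.6)/12 = 0.0426 per month; λ = ln(2)/m; D = treatment time capped at 24.
- E[e^(−hD)] = λ/(λ+h) × (1 − e^(−24(λ+h))) + e^(−24(λ+h)).
- Crude incidence = 1 − e^(−2h) × E[e^(−hD)], with e^(−2h) = 0.918.
- Mean time observable = (1 − e^(−24λ))/λ + 2.
- Expected number at risk at t months, from 10 subjects (52 over five groups is about 10 each) = 10 × e^(−ht) × e^(−λ(t−2)).

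| m (months) | Mean time observable (months) | Crude incidence | At risk of 10 at 3 / 6 / 12 months |
|---|---|---|---|
| 2 | 4.9 | 18.2% | 6.2 / 1.9 / 0.2 |
| 3 | 6.3 | 22.4% | 7.0 / 3.1 / 0.6 |
| 6 | 10.1 | 32.3% | 7.8 / 4.9 / 1.9 |
| 8 | 12.1 | 37.1% | 8.1 / 5.5 / 2.5 |
| 9 | 12.9 | 39.0% | 8.1 / 5.7 / 2.8 |
| 20 | 18.3 | 50.9% | 8.5 / 6.7 / 4.2 |

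Protocol 4.4 and the synopsis expect participation, including follow-up, to average about 12 to 18 months. In this model that corresponds to medians of about 8 to 20 months, and so to crude incidence of about 37% to 51%.

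**Second set of assumptions.** Take 33% as the 6-month risk. That is the order of magnitude Protocol 1.3.2.2 gives for Grade 3 or 4 treatment-related events on nivolumab plus ipilimumab in lung cancer; using it as a 6-month risk is an assumption. Crude incidence is then 22.7% with mean treatment of 2 months and 42.5% with 8 months. A simulated Kaplan-Meier estimate at 6 months (200,000 subjects) gives 33.1% and 33.0%. If the 6-month risk is 20%, crude incidence runs from 13.5% to 34.2% for means of 2 to 12 months; if it is 50%, from 35.3% to 66.2%.

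**The case against.** Several counter-arguments have force.

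- **Size.** A reader might infer that crude rates understate severe toxicity about twofold (39.0/18.2 = 2.1). That spread depends on medians of 2 to 3 months, which the documents do not give. At the stated average participation the spread is about 1.4-fold (50.9/37.1), and the crude figure lies close to or above the 12-month risk. The 12 to 18 months may predate the removal of survival follow-up in Amendment 3, but it is what the current text says.
- **Hazard shape.** The model is constant-hazard, while the concern is partly about late events. Onset patterns are not in the documents, so the effect by event type is not shown.
- **Decisions.** A reader might infer that dose escalation is compromised. It is not: Protocol 5.4.2 bases it on events within 28 days, and non-evaluable subjects are replaced. Protocol 4.2 and 9.3 also plan no between-group comparison and no formal tests.
- **Existing data.** A reader might infer that Phase 1 timing goes unreported. Onset dates are collected and listed, and exposure is tabulated by group and dose. With 52 subjects, individual timing can be read.
- **Precision.** With about 10 per group, a 12-month estimate leaves 0.2 to 1.9 subjects at risk when median treatment is 2 to 6 months. A by-group table at 12 months would be close to useless.
- **Design pattern.** Other outputs, such as the Kaplan-Meier figures, are also Phase 2 only, and omitting a life table for cells of 3 to 9 subjects was defensible when Phase 2 was expected.

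These points limit the size and shape the fix. They do not supply a Phase 1 estimate of severe-event risk by time.

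**Conclusion.** The gap is real and modest. The only planned time-to-onset safety summary will be empty, and the Phase 1 summary tables do not account for unequal time at risk. The mechanism is certain; its size is not, because the documents contain no Phase 1 treatment durations or onset data. The figures above rest on a constant hazard, exponential treatment time and leaving unrelated to toxicity risk. Under them, crude incidence for one and the same 40% 12-month risk ranges from 18% to 32% at assumed short medians, and from about 37% to 51% at the stated average participation. The documents do not support a claim of systematic understatement, or of any effect on escalation decisions. This is a worthwhile reporting improvement to the safety summary.

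**What to change.** Assign Table 3.2.28 to the Phase 1 full analysis set, with these specifications:

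- **Columns:** all subjects combined, and by treatment group with dose pooled, beside the crude number (%).
- **Estimates:** cumulative incidence at 3 and 6 months with numbers at risk and 95% confidence intervals; later times only where enough subjects remain.
- **Time origin:** first dose of INCAGN01949. For run-in Groups C and E, also from the first partner-drug dose at Cycle 3, among subjects who receive it.
- **Censoring:** end of adverse event collection. Treat death and new anticancer therapy as competing events, or show that as a sensitivity analysis, and say which is primary, since the two answer different questions.
- **Repeat** for first Grade 3 or higher immune-related event.

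The table is already marked standard, and SAP 8.2.1 requires missing onset dates to be queried. Appendix A allows changes to the table list without an SAP amendment if the nature of the analysis is unaffected. Because population, stratification and censoring rules change, a short documented note is safer. The cost is a little more programming. Intervals will be wide with about 10 subjects per group, so the all-subjects column will carry most of the information.

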3.3 Laboratory				
3.3.1	Summary of Laboratory Values – Hematology	Phase 2 FAS Population	X	
3.3.2.1	Summary of Hematology Laboratory Values in CTC Grade – To the Worst Abnormal Value	Phase 1 FAS Population		
3.3.2.2	Summary of Hematology Laboratory Values in CTC Grade – To the Worst Abnormal Value	Phase 2 FAS Population		
3.3.3	Summary of Laboratory Values – Chemistry	Phase 2 FAS Population	X	
3.3.4.1	Summary of Chemistry Laboratory Values in CTC Grade – to the Worst Abnormal Value	Phase 1 FAS Population		
3.3.4.2	Summary of Chemistry Laboratory Values in CTC Grade – to the Worst Abnormal Value	Phase 2 FAS Population		
3.4 Vital Signs				
3.4.1.1	Summary of Systolic Blood Pressure (mmHg)	Phase 1 FAS Population	X	
3.4.1.2	Summary of Systolic Blood Pressure (mmHg) – by Tumor Type	Phase 2 FAS Population	X	
3.4.2.1	Summary of Diastolic Blood Pressure (mmHg)	Phase 1 FAS Population	X	
3.4.2.2	Summary of Diastolic Blood Pressure (mmHg) – by Tumor Type	Phase 2 FAS Population	X	
3.4.3.1	Summary of Heart Rate (bpm)	Phase 1 FAS Population	X	
3.4.3.2	Summary of Heart Rate (bpm) – by Tumor Type	Phase 2 FAS Population	X	
3.4.4.1	Summary of Respiration Rate (bpm)	Phase 1 FAS Population	X	
3.4.4.2	Summary of Respiration Rate (bpm) – by Tumor Type	Phase 2 FAS Population	X	

Table No.	Title	Population	Standard	In-Text
3.4.5.1	Summary of Body Temperature (°C)	Phase 1 FAS Population	X	
3.4.5.2	Summary of Body Temperature (°C) – by Tumor Type	Phase 2 FAS Population	X	
3.4.6.1	Summary of Weight (kg)	Phase 1 FAS Population	X	
3.4.6.2	Summary of Weight (kg) – by Tumor Type	Phase 2 FAS Population	X	
3.5 ECG				
3.5.1.1	Summary of PR Interval (msec) From Local Lab 12-Lead ECG	Phase 1 FAS Population	X	
3.5.1.2	Summary of PR Interval (msec) From Local Lab 12-Lead ECG – by Tumor Type	Phase 2 FAS Population	X	
3.5.2.1	Summary of RR Interval (msec) From Local Lab 12-Lead ECG	Phase 1 FAS Population	X	
3.5.2.2	Summary of RR Interval (msec) From Local Lab 12-Lead ECG – by Tumor Type	Phase 2 FAS Population	X	
3.5.3.1	Summary of QT Interval (msec) From Local Lab 12-Lead ECG	Phase 1 FAS Population	X	
3.5.3.2	Summary of QT Interval (msec) From Local Lab 12-Lead ECG – by Tumor Type	Phase 2 FAS Population	X	
3.5.4.1	Summary of QRS Interval (msec) From Local Lab 12-Lead ECG	Phase 1 FAS Population	X	
3.5.4.2	Summary of QRS Interval (msec) From Local Lab 12-Lead ECG – by Tumor Type	Phase 2 FAS Population	X	
3.5.5.1	Summary of QTcB Interval (msec) From Local Lab 12-Lead ECG	Phase 1 FAS Population	X	
3.5.5.2	Summary of QTcB Interval (msec) From Local Lab 12-Lead ECG – by Tumor Type	Phase 2 FAS Population	X	
3.5.6.1	Summary of QTcF Interval (msec) From Local Lab 12-Lead ECG	Phase 1 FAS Population	X	
3.5.6.2	Summary of QTcF Interval (msec) From Local Lab 12-Lead ECG – by Tumor Type	Phase 2 FAS Population	X	

Table No.	Title	Population	Standard	In-Text
3.5.7.1	Summary of JTc Interval (msec) From Local Lab 12-Lead ECG	Phase 1 FAS Population		
3.5.7.2	Summary of JTc Interval (msec) From Local Lab 12-Lead ECG – by Tumor Type	Phase 2 FAS Population		
3.5.8.1	Summary of Heart Rate (beats/min) From Local Lab 12-Lead ECG	Phase 1 FAS Population	X	
3.5.8.2	Summary of Heart Rate (beats/min) From Local Lab 12-Lead ECG – by Tumor Type	Phase 2 FAS Population	X	
3.5.9.1	Summary of Alert Values of PR, QRS, QT, RR, and QTcF Interval Values From Local Lab 12-Lead ECG by Visit – by Treatment Group and Dose	Phase 1 FAS Population	X	X
3.5.9.2	Summary of Alert Values of PR, QRS, QT, RR, and QTcF Interval Values from Local Lab 12-Lead ECG by Visit – by Treatment Group and Dose	Phase 2 FAS Population	X	X

[figure not shown]
Figures

[figure not shown]
Figure No.	Title	Population
4.1 Efficacy		
4.1.1	Kaplan-Meier Estimates of Progression-Free Survival	Phase 2 FAS Population
4.1.2	Kaplan-Meier Estimates of Overall Survival	Phase 2 FAS Population
4.1.3.1	Swim Plot of Duration of Response – by Treatment Group	Phase 1 FAS Population
4.1.3.2	Swim Plot of Duration of Response – by Treatment Group and Tumor Type	Phase 2 FAS Population
4.1.4.1	Waterfall Plot of Percent Change From Baseline in Sum of Target Lesions – by Treatment Group and Dose	Phase 1 FAS Population
4.1.4.2	Waterfall Plot of Percent Change From Baseline in Sum of Target Lesions – by Treatment Group and Tumor Type	Phase 2 FAS Population
4.1.5.1	Spider Plot of Percent Change From Baseline in Sum of Target Lesions – by Treatment Group	Phase 1 FAS Population
4.1.5.2	Spider Plot of Percent Change From Baseline in Sum of Target Lesions – by Treatment Group and Tumor Type	Phase 2 FAS Population
4.2 Safety Data		
4.2.1.1	Line Graph of Selected Laboratory Values by Study Visit	Phase 1 FAS Population
4.2.1.2	Line Graph of Selected Laboratory Values by Study Visit	Phase 2 FAS Population
4.2.2.1	Box-and-Whisker Plot of Selected Laboratory Values by Study Visit	Phase 1 FAS Population
4.2.2.2	Box-and-Whisker Plot of Selected Laboratory Values by Study Visit	Phase 2 FAS Population

[figure not shown]
Listings

[figure not shown]
Listing No.	Title
2.1 Discontinued Subjects (Subject Disposition)	
2.1.1	Subject Enrollment and Disposition Status
2.1.2	Subject Inclusion and Exclusion Criteria Violations
2.2 Protocol Deviation	
2.2.1	Protocol Deviations and Violations
2.3 Data Excluded From █, Efficacy, and/or Safety Analyses	
2.3.1	Analysis Population
2.4 Demography and Baseline (Including Prior and Concomitant Medications)	
2.4.1	Demographic
2.4.2.1	Baseline Disease Characteristics for Phase 1 Solid Tumor Types
2.4.2.2	Baseline Disease Characteristics for Phase 2 – by Tumor Type
2.4.3	Disease History
2.4.4	Prior Radiation Treatment
2.4.5	Prior Systemic Therapy
2.4.6	Prior Surgery or Surgical Procedure
2.4.7	Medical History
2.4.8	Prior and Concomitant Medication
2.5 Efficacy █	
2.5.1.1	Best Overall Response With Confirmed CRs and PRs Under RECIST v1.1
2.5.1.2	Best Overall Response With Unconfirmed CRs and PRs Under RECIST v1.1
2.5.2.1	Best Overall Response With Confirmed CRs and PRs Under mRECIST
2.5.2.2	Best Overall Response With Unconfirmed CRs and PRs Under mRECIST
2.5.3	Overall Response Assessment
2.5.4	Response Assessment: Target Lesions
2.5.5	Response Assessment: Non-target Lesions
2.5.6	Response Assessment: New Lesions
2.5.7	ECOG status
█	█
2.6 Adverse Events (and Exposure)	
2.6.1.1	Study Drug Administration for INCAGN01949
2.6.1.2	Study Drug Administration for Nivolumab
2.6.1.3	Study Drug Administration for Ipilimumab
2.6.2	Adverse Events
2.6.3	Dose-Limiting Toxicities
2.6.4	Serious Adverse Events
2.6.6	Fatal Adverse Events
2.6.8	Adverse Events Leading to Discontinuation of INCAGN01949
2.6.9	Investigator-Identified Immune-Related Adverse Events
2.6.10	Infusion Reactions

[figure not shown]
2.7 Laboratory Data	
2.7.1	Clinical Laboratory Values – Hematology
2.7.2	Clinical Laboratory Values – Chemistry
2.7.3	Abnormal Clinical Laboratory Values
[REDACTED]	[REDACTED]
2.8 Vital Signs	
2.8.1	Vital Signs
2.8.2	Abnormal Vital Sign Values
2.8.3	Alert Vital Sign Values
2.9 ECG	
2.9.1	12-Lead Local ECG Values
2.9.2	Abnormal 12-Lead Local ECG Values
2.9.3	Alert 12-Lead Local ECG Values
